8.6.2. Analysis supporting secondary objectives

We will also evaluate the effect of FMD on risk factors for CVD and metabolic syndrome, defined as three of five of the following conditions: abdominal obesity, elevated fasting glucose, elevated blood pressure, high serum triglycerides, and low HDL cholesterol.

We will select clinically relevant cutoffs and compared normal and at-risk subjects for each risk factor: total cholesterol >199 mg/dl and LDL cholesterol levels >130 mg/dl are associated with an increased risk for CVD, a fasting glucose >99 mg/dl indicates impaired fasting glucose/prediabetes, and triglyceride levels >100 mg/dl as well as CRP >1 mg/liter are associated with increased risk for CVD. For serum IGF-1, no clinically relevant risk level has been established, but a number of epidemiological studies have associated IGF-1 levels above 200 ng/ml with various cancers (Levine et al., 2014; Pollack et al., 2007). We will therefore compare the effect of FMD cycles on subjects in the highest quartile of IGF-1 expression (>225 ng/ml) with that on subjects with IGF-1 levels \leq 225 ng/ml. The effect of FMD and FMD+LD treatments on these risk factors will be assessed also stratifying our sample by baseline BMI, SBP and DBP, fasting glucose, cholesterol, CRP and IGF-1.

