1.2. Fasting Mimicking Diet

The fasting-mimicking diet (FMD) is a 5-day meal program to be consumed every 1 to 6 months based on an authorized healthcare professional's recommendation. It is designed to promote the body's natural ability to protect, regenerate and rejuvenate itself. In clinical studies, FMD has been shown to reduce abdominal fat and maintain healthy levels of blood glucose, C-reactive protein (CRP), and insulin-like growth factor 1 (IGF-1) (Wei et al., 2017). Well-designed clinical trials, such as the study conducted by Houston et al. utilizing an independent review board (IRB) approved protocol, have demonstrated the safety and short-term benefits of plant-based nutraceuticals and food restriction in individuals with chronic hypertension (Houston et al., 2014).

A large ongoing randomized, open-label trial aimed at evaluating the effects of two different dietary interventions, FMD and LD, on body composition and cardiovascular (CV) biomarkers in a real word population (NCT05698654) is actually ongoing. This trial started in January 2024 will enrol 501 adult subjects between the ages of 30 and 65: 167 subjects randomized to the FMD arm with a 5-day meal program once every three months for a 6-month period (arm 1); 167 subjects randomized to follow the FMD plus a Longevity Diet program (FMD+LD) for a 6-month period (arm 2); 167 randomized to the control group (arm 3) that will continue their usual diet. On 2024,410, participants were enrolled and randomly assigned to FMD, FMD + LD, or control arm. Although preliminary data demonstrated the beneficial effects of such nutritional plans on body weight, BMI, body composition, and cardiovascular (CV) biomarkers, limited data is available on the long-term effects of these powerful nutritional interventions.

2. Study Objectives/Endpoints

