3.1.1. Inclusion Criteria

Individuals already included in the aforementioned previous studies *who were assigned to one of the 2 intervention arms: Fasting mimicking diet or fasting mimicking diet plus Longevity diet* and who completed the study less than 6 months prior to starting the new study. Blood tests and a nutritional assessment will be conducted, serving as the baseline for the new study.

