- Any sound medical, psychiatric and/or social reason which, in the opinion of the PI, would preclude safe participation in this study or interfere with compliance.
- Abnormal laboratory findings including: abnormal blood counts (haematocrit < 33% or > 47%; WBC < 3.0 or > 12.0 $\times 10^3/\text{mm}^3$; platelets < 140 or > 500 $\times 10^9/\text{L}$); abnormal kidney function test (creatinine > 2.5 mg/dL) or liver function test(s) (AST, ALT, alkaline phosphatase) > 1.5X the upper limit of normal; serum calcium > 11 mg/dL; serum K < 3.5 mEq/L; Na < 134 or > 148 mmolL⁻¹

3.1.8. *Women of Childbearing Potential*

Contraception: the effects of the study products on the developing human fetus have not been studied extensively. For this reason, women of childbearing potential must agree to use adequate contraception (hormonal or barrier method of birth control; abstinence) prior to study entry and for the duration of study participation. Females of childbearing potential will have a pregnancy test prior to receiving study products. Should a woman become pregnant or suspect she is pregnant while participating in this study, she should inform study staff and her primary care physician immediately.

Pregnancy: because there is an unknown but potential risk for adverse events in pregnant women during treatment with the study products, pregnant women are not eligible for study participation.

Breast-feeding: Because there is an unknown but potential risk for adverse events in nursing infants secondary to treatment of the mother with the study products, breastfeeding mothers are not eligible for study participation.

3.2. *Recruitment*

The participants will be identified within the intervention groups of the previous clinical studies (*Studio degli effetti della dieta mima-digiuno e della dieta della longevità sulla composizione corporea, fattori di rischio per malattie età-correlate e marcatori dell'invecchiamento in uno studio randomizzato 1 and 2*) who are willing to start a new study for other 12 months, and who completed the study less than 6 months prior to starting the new study and achieved the study's objectives. Blood tests and a nutritional assessment will be conducted, serving as the baseline for the new study. The recruitment period will last up to 3 years

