8.6. Study conclusions

Collected data from subjects will be reviewed to demonstrate that favourable changes are noted in biomarkers of body composition and age-related biomarkers with administration of the proprietary food products. Data will be evaluated for change from baseline over time within arms and for differences between the intervention arm and the control arm of previous study.

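### The same-marker at-risk versus normal comparisons in 8.6.2 can differ through regression to the mean alone, and 8.6.2 does not analyse the 50% retention endpoint of 2.2.2

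*Protocol*

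**What the plan says.** **Groups.** Section 8.6.2 states: "We will select clinically relevant cutoffs and compared normal and at-risk subjects for each risk factor". It then gives cutoffs for total cholesterol, LDL, fasting glucose, triglycerides and CRP. For IGF-1 it will "compare the effect of FMD cycles on subjects in the highest quartile of IGF-1 expression (>225 ng/ml") with the effect in the remaining participants. A last sentence adds "stratifying our sample by baseline BMI, SBP and DBP, fasting glucose, cholesterol, CRP and IGF-1".

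**Time point and comparator.** The cutoff sentences name no time point. Section 8.6 says "Data will be evaluated for change from baseline over time within arms", and section 3.1.1 says "Blood tests and a nutritional assessment will be conducted, serving as the baseline for the new study". Section 8.6 also provides "for differences between the intervention arm and the control arm of previous study", but 8.6.2 does not bring that arm into the risk groups. Under section 1.2 that arm belongs to a 6-month study, while the follow-up here is 12 months.

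**Endpoint.** Section 2.2.2 asks that at least half of 'one or more' of the parent-trial improvements be kept at one year. It lists nine: body mass, BMI, blood pressure, IGF-1, HbA1c, fasting glucose, LDL, total cholesterol and CRP. It adds trends in medication use. Section 8.6.2 mentions neither 50% retention nor the parent-trial improvement. It also omits HbA1c, body mass and medication use, and it brings in triglycerides, HDL, abdominal obesity and metabolic syndrome, which 2.2.2 does not list.

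**The concern.** (a) When the variable that forms the groups is also the outcome, a high T0 value partly reflects measurement error and temporary fluctuation. Those parts do not recur at 12 months, so the high group drifts down and the low group drifts up under any treatment or none. With everyone on FMD, the comparison cannot separate this drift from a larger diet effect in at-risk people, yet 8.6.2 labels the result the effect of FMD.

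(b) The stated secondary endpoint and the stated secondary analysis answer different questions. Where any one of nine factors suffices, chance gives each participant nine opportunities to succeed. A high success proportion could then be reported when nothing was maintained.

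**Working it through.** **Inputs from the Protocol.** 167 per intervention arm (1.2), drop-out 21% and 18%, and a maximum of 267 (8.1). The plan's own figure reproduces: 167 × 0.79 = 131.9 and 167 × 0.82 = 136.9; rounded down, 131 + 136 = 267.

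**Assumed.** A further loss of 20% in the new study: 267 × 0.8 ≈ 214. The Protocol gives no T0-T2 correlation and names no test for 8.6.2. I take correlations r from 0.5 to 0.9 and a Welch test of raw change. The at-risk share s = 0.25 follows the Protocol's own term, highest quartile, for IGF-1.

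**(a) Gap with no diet effect.** For a normal marker with equal mean and SD at both visits, cut at c = z(1 − s):

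gap = (1 − r) × φ(c) × [1/s + 1/(1 − s)], in population SD of the marker.

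With s = 0.25, c = 0.674 and φ(c) = 0.318, the multiplier is 1.271 + 0.424 = 1.695.

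| r | gap (SD) | raw change significant at 5%, n = 214 |
|---|---|---|
| 0.5 | 0.5 × 1.695 = 0.85 | about 100% |
| 0.7 | 0.3 × 1.695 = 0.51 | about 99% |
| 0.9 | 0.1 × 1.695 = 0.17 | about 68% |

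The percentages come from simulated trials. With 15-50% at risk they are 97-100% at r = 0.7 and 56-75% at r = 0.9. For a skewed marker left unlogged they fall to 87%, 63% and 24%. Regressing T2 on continuous T0 plus the group term rejects in 4.5-5.8% in the same no-effect settings. With a lognormal marker that model rejects in 36-48% unlogged and 5% logged.

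**(b) Nine chances.** Take three visits with within-person SD 1 and full regain by T2. A factor passes if the parent trial showed any observed improvement and T2 is at or below the midpoint of the parent baseline and parent end values. In the limit of no true parent improvement, a factor improves by chance in 1/2 of people and is then retained in 1/2, so 1/4 pass. With nine independent factors, 1 − 0.75^9 = 92%.

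With a true parent improvement that has been fully lost:

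| parent improvement (within-person SD) | one factor passes | any of nine, between-factor correlation 0.6 to 0 |
|---|---|---|
| 0.25 to 1.5 | 23-27% | 61-94% |
| 2 | 19% | about 53-85% |
| 3 | 11% | 37-64% |
| 4 | 5% | 21-38% |

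**The case against.** **The Protocol does not fix a T0 cut or a raw-change test.** True of the cutoff sentences. If groups were cut at the parent-trial baseline and change ran from T0 to T2, the gap is about zero with 5% rejection when that baseline correlates equally with both visits. Rejection is 10-28% if the correlation decays from 0.70 to 0.65 or 0.60. Sections 3.1.1 and 8.6 make T0 the natural reading, but the finding depends on it. Modelling detail may sit in an SAP; the contrast itself is already fixed in 8.6.2.

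**A reader might infer that all the stratified results in 8.6.2 are biased to this extent.** The documents do not support that. Most pairs in the last sentence of 8.6.2 cross different markers. With a stratifier-outcome correlation of 0.3 at both visits, the gap is zero and rejection 5% (11% if it decays to 0.25). That sentence also names FMD and FMD+LD, and a contrast of the former arms within a stratum cancels the effect (4% rejection at r = 0.7).

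**The previous control arm could absorb the drift.** Only in part. If its shorter interval gives correlation 0.80 against 0.70 here, a gap of 0.17 SD remains (18% rejection, 130 controls assumed).

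**A reader might also infer that 2.2.2 is wholly undefined.** That goes too far. Section 8.6.4 counts subjects reaching the primary endpoint, which has the same 50% form, so a participant-level reading is indicated. The chance-success problem arises on exactly that reading. The upper ends of the ranges in (b) assume nine uncorrelated factors, which weight and BMI are not.

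**Conclusion.** Both parts hold within limits.

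(a) For same-marker groups cut at T0, a difference in raw change between at-risk and normal participants is not evidence of a larger FMD effect. The direction of the bias holds at any correlation below 1. The size, 0.17 to 0.85 SD, rests on the assumed correlation, a normal marker and a top-quartile cut; the significance rates also rest on n = 214 and the Welch test. Cross-marker strata, former-arm contrasts and groups cut at the parent baseline are outside the finding. Nor does it show that FMD has no greater effect in at-risk people, only that this comparison cannot tell.

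(b) Section 8.6.2 does not analyse the endpoint in 2.2.2, and the any-one-of-nine wording makes success easy to reach by noise unless the parent improvement was large compared with within-person variation. These are secondary analyses, so the change is advisable and does not put the primary result in question.

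**What to change.** **Section 8.6.2, risk groups.** State that groups are cut at T0. For same-marker comparisons, do not interpret the difference in raw T0-T2 change. Model T2 on the continuous T0 value of that marker plus the group term, on the log scale for skewed markers such as CRP and triglycerides. Say that a larger fall in the at-risk group is not by itself evidence of a larger effect. *Cost:* the group term detects only a step beyond the linear baseline trend. At n = 214 its power for a 0.5 population SD step is about 70%, 85% and 100% at correlation 0.5, 0.7 and 0.9; for 0.3 SD it is 32%, 43% and 84%. For an effect linear in baseline it stays at 5%. The subgroup claim becomes weaker.

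**Sections 2.2.2 and 8.6.2, endpoint.** Delete 'one or more'. Report each factor as its own secondary endpoint, with weight and BMI counted once, because fixed height makes them retain the same share. In 8.6.2, analyse 50% retention against the parent baseline and parent end values for each factor that improved in the parent trial, and add the medication-use endpoint. Note that recruiting people "who completed the study less than 6 months prior to starting the new study and achieved the study's objectives" (section 3.2) may inflate the parent improvement.

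A study-level test of T2 against the parent midpoint can stand beside the participant proportion, not replace it. The contrast SD is √(1 + 0.25 + 0.25) = 1.22, so the standard error at n = 214 is 0.084. For a 0.5 within-person SD improvement at one-sided 2.5%, power is about 84-85% if it is fully kept (0.25/0.084 = 2.99) and 32% if 75% is kept (0.125/0.084 = 1.49). These figures assume measurement noise only. If true change varies between people with SD 0.5 to 1.0, they fall to 79-64% and 28-21%.

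*Cost:* a text change using values that 2.2.2 already needs. The results will look less favourable.

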8.6.3. Safety and Tolerability/Acceptability Evaluation

Collected data from subjects will be reviewed for occurrence of AEs and for data concerning hedonics, tolerability and acceptability of products. CMP and CBC data will be tallied and evaluated. This information will be considered in drafting any product instructions and warnings.

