3.3. Scheduled clinical visits

The assessment schedule (Table 1) lists all the assessments and when they are to be performed. Subjects will meet with study staff. When the visit doesn't include blood collection or BIA the visit can be made remotely. During the clinical visits, staff will review calendars, assess for signs and symptoms of adverse events, review compliance to the study product and answer any questions from the subject. Eligible participants will receive 3 different visits (Baseline visit (t0), and two follow-up visits (after 6 and 12 months from the baseline). Eligible participants will be telephonically contacted at the end of each FMD cycle (day 6) in order to assess signs and symptoms of adverse events, compliance to the nutritional intervention (see Appendix A, B), to answer to the questionnaire for dietary recall (see Appendix C).

4. Table 1 reports the timeline of the clinical visits and the activities scheduled. All data obtained from these assessments must be supported in the participant's source documentation.

	Screening Visit	Baseline visit (T ₀)	Follow-up visit 1 (T ₁)	Follow-up visit 2(T ₂)
Informed Consent	✓			
Review Eligibility Criteria	✓			
Start of intervention				
Physical examination ¹		✓	✓	✓
Vital Signs ²	✓	✓	✓	✓
BIA		✓	✓	✓
Peripheral Blood for genetic analysis		✓		✓
Hematological analyses ³		✓		✓
Pregnancy test	✓	✓		✓
AE and SAE collection		✓	✓	✓
Primary and secondary endpoints assessment		✓	✓	✓
Medications	✓	✓		✓

¹ height, weight (dress weight), waist and hip circumferences. ² Body temperature, blood pressure, pulse, respiratory rate. ³ Lipid profile (total cholesterol, LDL-cholesterol, HDL-cholesterol and triglycerides, serum/plasma, albumin, alkaline phosphatase, insulin-like growth factor 1 (IGF-1), Insulin-like growth factor-binding protein 1 (IGFBP1), creatinine, insulin, C-reactive protein (CRP),

aspartate aminotransferase (AST), alanine aminotransferase (ALT), homocysteine, glucose, glycosylated hemoglobin (HbA1c).

Screening and Baseline visit

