Potential participants already subjected to a 5-day fasting-mimicking diet (FMD) program either alone or in combination with the longevity diet previously enrolled in one of the two interventional arms and who completed the clinical study NCT05698654 less than three months before the enrolment period will be contacted *via* telephone to determine preliminary eligibility and interest. Once participants meet all inclusion/exclusion criteria, they will be offered by study staff the opportunity to learn more about the research opportunity before any procedure is performed. Participants meeting eligibility will be then invited to attend a baseline and two follow-up visits

Baseline visit will include measurement of height, weight, and vital signs (body temperature, blood pressure, pulse, respiratory rate), completion of medical history questionnaire, review of medical history and current medications, and collection of fasting blood (12 mL: 6 mL for serum, 6 mL for plasma). Blood testing will include: complete blood count (CBC), glycated hemoglobin (HbA1c), glucose, insulin, lipid profile (total cholesterol, LDL-cholesterol, HDL-cholesterol and triglycerides), AST (GOT), ALT (GTP), alkaline phosphatase, creatinine, reactive C protein (PCR), albumin, insulin, IGF-1, IGFBP1, homocysteine as well as a urine pregnancy test in females of child-bearing potential. Fasting is defined as 12 hours of refraining from consumption of food and beverages though unlimited consumption of water is allowed and encouraged. Participants will be given three boxes of FMD together with ketone test strips to self-monitor urinary ketone bodies during the FMD cycles. Detailed information on the FMD plans will be also given during the visit. Baseline visit will also include body composition assessment using Bioelectrical Impedance Analysis (BIA), measurement of height, weight, and vital signs, medical history, current medications and a collection of fasting blood for the genetic analysis (25 mL: 7.5 mL for serum, 7.5 mL for plasma, 10 mL for white blood cells). Note, the typical draw volume for blood donation in Italy is ~450 mL. Blood testing information will be also retried from the screening visit.

Follow-up visits

The follow-up visits will be carried out after three (follow-up visit 1) and five (follow-up visit 2) FMD cycles (6 and 12 months), in order to evaluate the progress of the trial.

Follow-up visit 1

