During the first follow-up visit, the study staff will assess the signs and symptoms of adverse events and review compliance to the FMD program. The visit will also include body composition assessment using BIA, measurement of height, weight, and vital signs, medical history and current medications. Participants will receive the FMD boxes for the remaining two cycles together with the ketone test strips for self-monitoring of urinary ketone bodies during the FMD cycles.

Follow-up visit 2

During the second follow-up visit, the study staff will assess the signs and symptoms of adverse events and review compliance to the FMD program. This visit will also include body composition assessment using BIA, measurement of height, weight, and vital signs, medical history and current medications. In addition, a collection of fasting blood for haematological and for the genetic analyses will be performed.

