6.1. Hematological analyses

Complete metabolic and lipid panels (after overnight fasting) will be completed at the Istituto Clinico “[name]. R. De Blasi” srl, [name], in Reggio Calabria and analyzed immediately after the blood draw of each visit. Clinical and biochemical evaluations include lipid profile (total cholesterol, LDL-cholesterol, HDL-cholesterol and triglycerides), serum/plasma, albumin, alkaline phosphatase, insulin-like growth factor 1 (IGF-1), Insulin-like growth factor-binding protein 1 (IGFBP1), insulin, C-reactive protein (CRP), aspartate aminotransferase (AST), alanine aminotransferase (ALT), homocysteine, glucose, glycosylated hemoglobin (HbA1c).

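### Section 8.6.3 evaluates blood-count data, but no list orders a complete blood count after baseline

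*Protocol*

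**What the plan says.** The safety analysis in Protocol 8.6.3 reads "CMP and CBC data will be tallied and evaluated". It gives no time point, and it says the information will feed into product instructions and warnings. Section 7.4.1 says that safety assessment covers haematological as well as chemical parameters, again without naming a test or a visit.

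The tests themselves are set out in four places:

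- **Baseline visit text (section 3.3 and the visit descriptions after Table 1):** "Blood testing will include: complete blood count (CBC), glycated hemoglobin (HbA1c), glucose, insulin, lipid profile", followed by further chemistry that includes creatinine, AST, ALT and alkaline phosphatase.
- **Follow-up visit 2 text (T2, 12 months):** "a collection of fasting blood for haematological and for the genetic analyses will be performed". The haematological tests are not listed there.
- **Table 1:** the row for haematological analyses is ticked at T0 and T2. Footnote 3 defines it as lipids, albumin, alkaline phosphatase and a run of hormones and chemistry ("Insulin-like growth factor-binding protein 1 (IGFBP1), creatinine, insulin, C-reactive protein (CRP"), ending with AST, ALT, homocysteine, glucose and HbA1c.
- **Section 6.1, under the heading for haematological analyses:** complete metabolic and lipid panels, then nearly the same list, this time without creatinine ("Insulin-like growth factor-binding protein 1 (IGFBP1), insulin, C-reactive protein (CRP").

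**The concern.** An evaluation of blood counts meant to inform warnings about a product needs counts taken after exposure to it. The baseline count precedes all five FMD cycles of this study. It describes who entered, perhaps with some trace of the earlier trial's cycles, but says nothing about the year under study.

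If the laboratory runs exactly what footnote 3 and 6.1 list, T2 yields chemistry and hormones but no haematocrit, white cells or platelets. The loss would be permanent. Section 6.2 stores blood as separated fractions or frozen aliquots, which do not preserve a routine count for later. A SAP cannot repair this either, because which tests are drawn at which visit is protocol content and a SAP can only analyse what was measured.

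**Working it through.** The plan gives no figure to reproduce. The check sets the places that govern laboratory tests side by side.

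| Place in the Protocol | Applies to | Blood count | Creatinine | Na, K, calcium |
|---|---|---|---|---|
| Baseline visit text | T0 | named | named | not named |
| Table 1 footnote 3 | T0 and T2 | not named | named | not named |
| Section 6.1 | visits with a draw | not named | not named | not named; the opening phrase on complete metabolic panels may cover them |
| Follow-up visit 1 text | T1 | no blood scheduled | – | – |
| Follow-up visit 2 text | T2 | only the word haematological | – | – |
| Section 7.4.1 | no visit given | haematological monitoring, no test named | – | – |
| Section 8.6.3 | no time given | CBC to be evaluated | CMP to be evaluated, contents not given | as for creatinine |

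1. *What defines the T2 bloods?* The T2 text uses the word haematological without listing tests. The Protocol gives that term content twice, in footnote 3 and in 6.1. Both times it is a chemistry, lipid and hormone panel.
2. *Scheduled CBCs per participant, read literally:* T0 = 1 (visit text), T1 = 0 (no blood), T2 = 0 (neither list). Post-baseline total: 0 + 0 = 0.
3. *Scheduled CBCs if a T2 count is intended:* T0 = 1, T1 = 0, T2 = 1. Post-baseline total: 0 + 1 = 1, and a T0-to-T2 comparison is possible.
4. *What is safe under either reading:* creatinine, AST, ALT and alkaline phosphatase stand in the baseline text and in footnote 3, so they can be compared between T0 and T2.

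**The case against.** The strongest reply is that the lists are not meant to be exhaustive. Footnote 3 covers T0 as well as T2, yet the baseline text orders a CBC that the footnote omits, so the footnote is incomplete for the very row it defines. Section 6.1 introduces its list as what the evaluations include. The T2 text, 7.4.1 and 8.6.3 all point to a blood count. On the most coherent reading a T2 CBC is intended and the lists were not updated. This stands as a statement of probable intent, and it is why the point is minor. It does not remove the mismatch, because a laboratory works from the lists and neither list orders the test.

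A second reply is that 8.6.3 sets no time point and plans only a descriptive tally, so baseline counts would satisfy it. That is true to the letter, but such a tally cannot inform warnings about exposure in this study.

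A reader might infer more, and the documents do not support it:

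- *That electrolytes and calcium go unmeasured.* They have entry limits in section 3.1.7 ("serum calcium > 11 mg/dL; serum K < 3.5 mEq/L") and no list names them, but the complete metabolic panels in 6.1 plausibly cover them. Creatinine is missing from 6.1 but stands in footnote 3.
- *That every laboratory parameter with an entry limit should reappear at T2.* Those limits govern eligibility. Nothing requires them to be measured again.
- *That 6.1 contradicts Table 1 about T1.* The phrase "analyzed immediately after the blood draw of each visit" can mean each visit that has a draw. Section 3.3 foresees visits without blood collection, and Table 1 agrees with the T1 text ("The visit will also include body composition assessment using BIA, measurement of height, weight, and vital signs, medical history and current medications").
- *That the laboratory criterion in 7.4.5 cannot work.* That section promises no scheduled test during treatment, and under 7.1 an abnormal laboratory finding from any source can count as an adverse event.

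**Conclusion.** The point holds as a minor inconsistency in the safety schedule. The Protocol commits to evaluating CBC data and to haematological monitoring but names a CBC only at baseline. The number of scheduled post-baseline counts per participant is 0 if footnote 3 and 6.1 are followed as written, and 1 if a T2 CBC is intended. The second is the more likely intention, but the lists do not express it.

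The conclusion rests on one assumption: that whoever orders the T2 tests follows the written lists. The consequence is limited to the CBC part of 8.6.3. A blood count is neither a primary nor a secondary endpoint in section 2.2, and adverse-event review continues at every visit.

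**What to change.** Add CBC to Table 1 footnote 3 and to section 6.1, and let the baseline visit text refer to the same list, so that T0 and T2 use one panel on the existing draws. For consistency, name the components meant by CMP in both places: creatinine, sodium, potassium and calcium.

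The cost is one routine test on a draw already scheduled at T2, plus the wording edits. If the laboratory's metabolic panel does not already include sodium, potassium and calcium, those are added to the same sample. No extra visit or draw is needed. If a T2 CBC is in fact not wanted, the alternative is to limit 8.6.3 to the tests that are scheduled.
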